6.4. Triplicate 12-Lead Electrocardiograms

Triplicate 12-lead ECGs will be obtained after the participant has been in the supine position for ≥ 5 minutes. ECG measurements will be collected at the timepoints identified in [Appendix 14.1](#), [Appendix 14.2](#), [Appendix 14.4](#) and [Appendix 14.5](#).

All ECGs will be analyzed from a clinical safety basis (without intensive QT analysis). The clinical significance of ECG changes will be determined by the investigator after review of the ECG report in relation to the participant's medical history, PE, and concomitant medications and documented on the eCRF.

For summaries of quantitative triplicate 12-lead ECG parameters, the average of the triplicate 12-lead ECG measurements will be used for the determination of baseline and calculation of summary statistics.

For interpretation of triplicate 12-lead ECGs, baseline will be defined as the best case of the last non-missing triplicate measurements (including repeated and unscheduled measurements) before the start of first study drug administration. For calculation of post-dose summary statistics, the worst case of the non-missing triplicate measurements will be used. The order of interpretation

for 12-lead ECGs (best to worst case): Normal; Abnormal, Not Clinically Significant; Abnormal, Clinically Significant. Interpretations of Indeterminate, Not Evaluable, or Unknown will not be considered when determining the worst or best case.

Actual values and changes from baseline for quantitative ECG results will be summarized at each time point using descriptive statistics.

Shift from baseline in ECG interpretation and clinical significance will be summarized by visit using the frequency count and percentage of participants in each category.

In addition, the number (percentage) of subjects with at least 1 post-baseline abnormal ECG result in corrected QT interval calculated using Fridericia's formula (QTcF) interval, PR, QRS or HR will be summarized. Clinically abnormal ECG results will be categorized as follows:

Absolute QTcF interval prolongation:

- QTcF interval >450 msec
- QTcF interval >480 msec
- QTcF interval >500 msec

Change from baseline in QTcF interval:

- QTcF interval increases from baseline >30 msec
- QTcF interval increases from baseline >60 msec
- PR < 120 msec
- PR > 200 msec
- QRS < 60 msec
- QRS > 100 msec
- HR < 60 bpm
- HR > 100 bpm

All 12-lead ECG data will be presented in a data listing, 12-Lead Electrocardiogram data for participants with abnormal post-baseline result in QTcF interval will also be listed.

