- ^d Vital signs will be recorded after the participant has been resting for at least 5 minutes in the supine position. On dosing days, vital signs will be recorded prior to infusion (pre-dose) and within 15 minutes after the end of infusion, and once at all other specified time points as indicated. Weight (kg) will be collected at the same visits that vital signs are taken.
- ^e Triplicate 12-lead ECGs will be obtained after the participant has been in the supine position for ≥ 5 minutes. On specified dosing days ECG will be obtained prior to study drug administration and within 60 minutes after the end of infusion, and once at all other specified time points as indicated. Additional ECG monitoring must be performed during the treatment period if clinically indicated.
- ^f Details on timing of vital signs, serum PK samples, triplicate ECGs, serum ADA samples, progranulin plasma samples, exploratory plasma PD biomarker samples, whole blood samples for WBC analysis, and exploratory whole blood PD biomarker samples are provided in [Table 6](#).
- ^g Samples will be collected prior to study drug administration (if applicable).
- ^h If the lumbar puncture is moved to a different visit, the coagulation panel will be moved to the visit immediately preceding the new lumbar puncture visit.
- ⁱ Serology testing will include anti-HCV, anti-HIV, HIV antigen, HBsAg, and total hepatitis B core antibody.
- ^j All women of childbearing potential will have a serum pregnancy test at screening. Urine pregnancy tests will be performed at specified subsequent visits. If a urine pregnancy test is positive, it must be confirmed by a serum pregnancy test.
- ^k Blood serum samples will be collected for determination of ADA prior to study drug administration (if applicable). Additional ADA samples should be collected in participants with signs and symptoms of infusion-related reactions. A sample of blood should be obtained for PK serum and ADA assessment of AL001, and testing should be performed for C-reactive protein, tryptase, and Interleukin 6 (IL-6).
- ^l Cerebrospinal fluid samples will be collected via lumbar puncture prior to study drug administration (if applicable). The timing of lumbar punctures may be adjusted as determined by Alector's review of exploratory PD biomarkers. *GRN* mutation carriers previously treated in Study AL001-1 may not be required to repeat the CSF assessment if it has been performed within 3 months prior to screening.

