1.1. Objectives and Endpoints

Table 1: Part 1 (Treatment Period): Study Objectives and Endpoints

	Objective(s)	Endpoint(s)
Primary	The primary objective of the treatment period of the study is to evaluate the safety and tolerability of IV administration of AL001 over 96 weeks in asymptomatic and symptomatic carriers of a GRN mutation causative of FTD and in symptomatic carriers of a C9orf72 mutation causative of FTD.	Primary Safety Endpoints: To assess the potential effect of cumulative exposure on the safety profile of AL001, the following will be evaluated by dose, such as by using tertiles of the actual dose (normalized to weight) received: 
• Incidence, nature, and severity of AEs and SAEs• Incidence of treatment discontinuations and study discontinuations due to AEs• Physical examination abnormalities• Neurological examination abnormalities• Changes in vital signs from baseline over time• Changes in ECGs from baseline over time• MRI abnormalities after dosing relative to baseline• Changes in clinical laboratory tests from baseline over time• Sheehan Suicidality Tracking Scale (Sheehan-STS)• Incidence of ADAs to AL001
Secondary	The secondary objectives of the treatment period of the	

	
study are to evaluate the effect of IV administration of AL001 over 96 weeks in asymptomatic and symptomatic carriers of a GRN mutation causative of FTD and in symptomatic carriers of a C9orf72 mutation causative of FTD on the following:
	
	
Secondary PK Objective:
 
 • PK 	
Secondary PK Endpoints:
 
 • Serum concentration of AL001 at specified time points • AL001 PK parameters (if data permit) ◦ C_{max} ◦ C_{trough} ◦ AUC_{ss}
	
Secondary PD Biomarker Objectives:
 
 • Longitudinal plasma and CSF PGRN concentration levels • Longitudinal levels of Sortilin in WBCs 	
Secondary PD Biomarker Endpoints:
 
 • The overall change from baseline in PGRN in CSF • The overall change from baseline in PGRN in plasma • The overall change from baseline in Sortilin in WBCs in plasma

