Baseline will be defined as the last non-missing assessment, including repeated and unscheduled measurements, prior to the start of first study drug administration.

Due to the high rate of participant attrition over the study duration and small FTD cohort sizes, time points beyond week 49 will not be included in the cohort level summary of the figures.

All CIs will be 2-sided and performed using a 5% significance level except for PK parameters for which, 90% CI and geometric mean will be used. All p-values will be presented to 3 decimal places and values less than 0.001 or greater than 0.999 will be presented as <0.001 and >0.999, respectively. As the objectives of the study are exploratory in nature no adjustments for multiplicity will be made.

No formal significance testing will be performed.

Analysis visit windows will be applied for COA and Biomarker analysis. A detailed explanation about the analysis visit windows will be described in the specific section of each analysis,

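### The primary endpoint of ADA incidence has no planned count of participants who become positive across visits; secondarily, the ECG interpretation shift table uses a different reading rule before and after dosing.

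*SAP*

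**What the plan says.** **ADA.** SAP 1.1 lists "Incidence of ADAs to AL001" among the primary endpoints of Part 1 and of Part 2. SAP 6.7 plans, for each visit, the number and percentage of participants in each result category, with titer statistics and listings. Samples taken because of an infusion-related reaction are left out of the summary and listed separately. Protocol 8.4.2.10 asks for a summary by time point and nothing further. Neither document plans a count across visits or defines treatment-emergent ADA.

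**ECG interpretation.** SAP 6.4 orders readings as normal, abnormal not clinically significant (NCS), and abnormal clinically significant (CS). Before dosing, "baseline will be defined as the best case of the last non-missing triplicate measurements". After dosing the rule reverses: "For calculation of post-dose summary statistics, the worst case of the non-missing triplicate measurements will be used". Both feed one table: "Shift from baseline in ECG interpretation and clinical significance will be summarized by visit using the frequency count". For the quantitative parameters the rule is symmetric: "the average of the triplicate 12-lead ECG measurements will be used for the determination of baseline and calculation of summary statistics".

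**ADA schedule.** SAP 14.1 and Protocol Table 6 show an ADA sample at every visit from Week 1 to Week 53. SAP 14.3 leaves the ADA column blank at Weeks 5, 9, 17, 21, 29, 33, 41 and 45.

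**The concern.** The incidence of ADA is ordinarily read as the number of participants who became positive. A series of by-visit percentages does not contain that number, because it does not show whether the same people are positive each time. Denominators will also shrink: SAP 2 gives as its reason for truncating the figures "Due to the high rate of participant attrition over the study duration and small FTD cohort sizes". The result that a primary endpoint asks for would have to be compiled by hand from listings, under rules for baseline positives and unscheduled samples that nobody had fixed in advance.

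For the ECG table, someone who reads normal, normal, abnormal both before and after dosing is tabulated as having worsened. The study has one arm, so no control column shows how much of the shift comes from the rule alone.

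**Working it through.** **The plan's own figure.** Protocol 8.1 and SAP 2.1 give the chance of at least one finding in 40 participants. With 1 − (1 − p)^40 at p = 0.1%, 1%, 5% and 10%, I get 3.92%, 33.10%, 87.15% and 98.52%, in agreement with the stated 3.9%, 33.1%, 87.1% and 98.5%. The present point does not depend on these values. The documents give no ADA rate and no rate of disagreement within ECG triplicates, so the rates below are assumptions.

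**ADA 1: what by-visit counts determine.** If n_v participants are positive at visit v, the number ever positive lies between max(n_v) and the sum of n_v, capped at the number tested. Protocol Table 6 has 18 post-baseline ADA visits in Part 1: V2 to V15 (14), V17, V20, V23 and V26. Assume 2 of 40 (5%) are positive at each, with complete sampling. The bounds are 2 and 18 × 2 = 36 participants, or 5% and 90%.

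**ADA 2: role of persistence.** Keep 5% at each visit and let s be the chance that a positive participant is still positive at the next visit. The chance of turning positive between visits is then a = 0.05(1 − s)/0.95, and the share ever positive is 1 − 0.95(1 − a)^17.

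| s (assumed) | a | Ever positive |
|---|---|---|
| 0.95 | 0.0026 | 9.2% |
| 0.80 | 0.0105 | 20.6% |
| 0.50 | 0.0263 | 39.6% |

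The by-visit table is the same in all three rows.

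**ADA 3: reaction-triggered samples.** Protocol Tables 4 to 9 give 25 dosing visits in Part 1 (V1, V3 to V26) and 25 in Part 2 (V27 to V51). No ADA sample is scheduled at V16, V18, V19, V21, V22, V24 and V25 (7), or at any Part 2 dosing visit except V32, V38, V44 and V51 (25 − 4 = 21). At 7 + 21 = 28 of 50 dosing visits, a reaction-triggered sample would be the only one. How often this would occur is unknown.

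**ADA 4: earlier exposure.** Protocol 1.2.2.1 reports 6 asymptomatic and 8 symptomatic *GRN* carriers dosed in AL001-1, so up to 14 may enter already exposed. Under Protocol 3.1, asymptomatic participants can enroll only from that study, so the whole aFTD-*GRN* cohort is in this position. Protocol 1.3.2 says that ADAs have developed on AL001.

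**ECG 1: a result that needs no model.** Suppose the pattern of readings does not change and the number of evaluable tracings is equal. Baseline counts as normal unless all three tracings are abnormal; a post-dose triplicate counts as normal only if all three are normal. Then

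net shift to abnormal = [1 − P(all abnormal)] − P(all normal) = P(mixed triplicate).

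Each 10% of mixed triplicates adds 10 percentage points of net worsening among participants with an ECG at that visit. Any single rule used at both times gives a net of zero.

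**ECG 2: illustration on assumed rates.** Let the chance p that a tracing is abnormal vary between participants as a beta distribution with mean 0.20 and within-participant correlation 0.5, and let q = 1 − p. Then E[p³] = 0.088, E[q³] = 0.672 and E[p³q³] = 0.003.

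- Mixed triplicates: 1 − 0.088 − 0.672 = 24.0%.
- Planned rule: 24.0% + 0.3% = 24.3% shift to abnormal and 0.3% shift back.
- Worst of three at both times: E[q³] − E[q⁶] = 0.672 − 0.592 = 8.0% each way.

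Over means of 2% to 30% and correlations of 0.3 to 0.9, the planned rule gives 0.6% to 45% to abnormal and at most 0.6% back.

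**ECG 3: which triplicate.** Protocol Table 4, footnote e: "On specified dosing days ECG will be obtained prior to study drug administration and within 60 minutes after the end of infusion". Protocol Tables 6 and 9 show two triplicates at eight dosing visits after V1 (V8, V14, V20, V26, V32, V38, V44, V51). The SAP reports the shift by visit and does not say whether one or both feed the row.

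**Schedule.** With SAP 14.3, the 18 post-baseline Part 1 samples become 18 − 8 = 10.

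**The case against.** A reader might infer that the ADA analysis counts no participants. That is not so: SAP 6.7 counts them at each visit, baseline positives should appear in the baseline row of their cohort, and everything is listed. What stands is that no table links the visits, so the number who became positive can be had only by working through the listings.

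On the ECG, the best/worst rule is a prespecified choice that errs toward showing harm in a descriptive study without testing. It is not an arithmetic error, and it does not hide a safety signal. A reader might also infer that it distorts shifts to CS as much as shifts to NCS. Exclusion 12 in Protocol 4.1.2 bars clinically significant ECG abnormalities at entry, so few baseline tracings should be CS. If none are, best and worst fall on the same side of that cut, and the effect lies mainly in the move from normal to NCS.

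Nor are the ECG safety results at large affected. Quantitative changes use triplicate means. The counts of participants with an abnormal QTcF, PR, QRS or HR do not use the rule. Confirmed, clinically significant findings are reported as AEs under Protocol 7.3. SAP 6.4 adds that "All 12-lead ECG data will be presented in a data listing". Finally, if the three readings of a triplicate rarely differ, the excess is near zero. All of this stands and makes the ECG point secondary.

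The mismatch with SAP 14.3 is a matter of correction, since footnote f of SAP 14.1 already refers ADA timing to Protocol Table 6.

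**Conclusion.** The ADA point holds and should lead. A primary endpoint in both parts has no planned table giving the number of participants who became positive, and no rule for those positive at baseline. The bounds, from the largest by-visit count to the sum, follow by logic. The figures of 2 to 36 participants and 9.2% to 39.6% rest on an assumed 5% at each visit; they show that the table leaves the answer open and do not forecast it.

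The ECG point holds for the interpretation shift table only. Its direction is certain whenever mixed triplicates occur: unchanged readings are shown as net worsening. Its size is unknown, and the 24.3% against 0.3% should not be read as an expected result.

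The change is worth making before database lock. Nothing here shows that safety data are lost or that a conclusion would be reversed.

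**What to change.** 1. **ADA (main).** Add one table to SAP 6.7, by cohort and overall: the number and percentage of participants who are ADA-negative at the SAP-defined baseline (last non-missing value before first dose) and positive on any post-baseline sample. Give it with and without unscheduled samples, because participants with reactions have more chances to test positive. Show baseline-positive participants separately with their titers over time. Keep the by-visit table.
2. **ECG (secondary).** In SAP 6.4 use one interpretation rule at both times, for example the worst evaluable reading. Apply it separately to the pre-dose and end-of-infusion time points, so that each row rests on one triplicate as baseline does. Keep the best/worst table as a labelled conservative display.
3. **Schedule (minor).** Correct the ADA column of SAP 14.3 to agree with SAP 14.1 and Protocol Table 6.

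The cost is SAP wording, one additional ADA table and one additional ECG table, all from data already collected. The drawback of worst-at-both is that it can mask a new abnormality in someone with one abnormal baseline tracing: 3E[pq²] = 14.4% of participants under the assumed 20% and 0.5, and 0.3% to 26.8% over the assumed range. The retained best/worst table covers those cases.

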2. STUDY OBJECTIVES AND ENDPOINTS

The objectives and endpoints of this study are provided in [Table 1](#) and [Table 2](#).

Table 1: Part 1 (Treatment Period): Study Objectives and Endpoints

	Objective(s)	Endpoint(s)
Primary	The primary objective of the treatment period of the study is to evaluate the safety and tolerability of IV administration of AL001 over 96 weeks in asymptomatic and symptomatic carriers of a GRN mutation causative of FTD and in symptomatic carriers of a C9orf72 mutation causative of FTD.	
Primary Safety Endpoints:
 
To assess the potential effect of cumulative exposure on the safety profile of AL001, the following will be evaluated by dose, such as by using tertiles of the actual dose (normalized to weight) received:
 
 • Incidence, nature, and severity of AEs and SAEs • Incidence of treatment discontinuations and study discontinuations due to AEs • Physical examination abnormalities • Neurological examination abnormalities • Changes in vital signs from baseline over time • Changes in ECGs from baseline over time • MRI abnormalities after dosing relative to baseline • Changes in clinical laboratory tests from baseline over time • Sheehan Suicidality Tracking Scale (Sheehan-STS) • Incidence of ADAs to AL001
Secondary	The secondary objectives of the treatment period of the study are to evaluate the effect of IV administration of AL001 over 96 weeks in asymptomatic and symptomatic carriers of a GRN mutation causative of FTD and in symptomatic carriers of a C9orf72 mutation causative of FTD on the following:	
	
Secondary PK Objective:
 
 • PK 	
Secondary PK Endpoints:
 
 • Serum concentration of AL001 at specified time points • AL001 PK parameters (if data permit) 
 ◦ C_{max} ◦ C_{trough} ◦ AUC_{ss}
	
Secondary PD Biomarker Objectives:
 
 • Longitudinal plasma and CSF PGRN concentration levels • Longitudinal levels of Sortilin in WBCs 	
Secondary PD Biomarker Endpoints:
 
 • The overall change from baseline in PGRN in CSF • The overall change from baseline in PGRN in plasma • The overall change from baseline in Sortilin in WBCs plasma

Table 1: Part 1 (Treatment Period): Study Objectives and Endpoints (Continued)

	Objective(s)	Endpoint(s)

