12. History of or current abnormal ECG that is clinically significant, including atrial fibrillation, complete left bundle branch block, second- or third-degree atrioventricular block, or evidence of acute or subacute myocardial infarction or ischemia.
13. History of ventricular dysrhythmias or risk factors for ventricular dysrhythmias such as structural heart disease (e.g., severe left ventricular systolic dysfunction, left ventricular hypertrophy) or clinically significant electrolyte abnormalities (e.g., hypokalemia, hypomagnesemia, hypocalcemia). Note: Participants with premature ventricular contractions are eligible to participate.
14. Contraindication to lumbar dural puncture, including coagulopathy, concomitant anticoagulation (except for a platelet inhibitor such as aspirin), thrombocytopenia, or other factor that precludes safe lumbar puncture.
15. Dementia or a milder, symptomatic syndrome (e.g., mild cognitive impairment, mild behavioral impairment, or mild motor impairment) due to a condition other than FTD,

including, but not limited to, Alzheimer's disease, Parkinson's disease, dementia with Lewy bodies, Huntington disease, or vascular dementia.

16. History or presence of clinically evident vascular disease potentially affecting the brain (e.g., clinically significant carotid or vertebral artery stenosis or plaque; cerebral hemorrhage or infarct greater than 1 cm³; 3 or more lacunar infarcts in any location); cerebral contusion; encephalomalacia; intracranial aneurysm; arteriovenous malformation; subdural hematoma; hydrocephalus; space occupying lesions (e.g., abscess or brain tumor such as meningioma) that has the potential to affect cognitive function; or intracranial tumor that is clinically relevant (e.g., glioma, cerebral metastasis).
17. History of severe, clinically significant (persistent neurologic deficit or structural brain damage) CNS trauma.
18. Prospective participant resides in a skilled nursing facility, convalescent home, or long-term care facility at screening and requires continuous nursing care (i.e., >3 months). Participants from the Phase 1 study (AL001-1) who have since moved to one of these facilities and require continuous nursing care are not eligible to continue to this study (AL001-2).

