5.3. Study Drug Administration

Study drug administration data will be summarized for the Safety population. The summary will include duration of exposure to study drug (in days), the number of doses received, treatment compliance, number of doses interrupted, discontinued, and total dose (mg) received.

Duration of exposure to study drug (days) is defined as the total number of days a participant is exposed to AL001 and will be calculated as the total number of days from the first dose date (Study Day 1) to the last dose date + 28 days, regardless of any temporary interruptions in study drug administration. 28 days is the study treatment administration (IV) interval.

Treatment compliance will be defined as the total cumulative received dose (mg/kg) divided by the total cumulative expected dose (mg/kg) up to the last dose, and then multiplied by 100. The total cumulative expected dose will be the sum of the expected doses while they are on study treatment across all planned study days, up to the date of withdrawal, if participant discontinued study drug early.

The function is as follow:

Treatment Compliance=100×(total cumulative received dose (mg/kg))/(total cumulative expected dose (mg/kg))

Study drug administration data will be presented in a listing. Any drug administration interruption and reasons will be listed.

6. Safety Analysis

All analyses of safety data will be conducted using the Safety population. All safety data will be listed.

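### The nine absolute ECG cut-offs in SAP 6.4 are counted without regard to baseline, so participants already beyond a cut-off before dosing enter the post-baseline abnormality rate

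*SAP*

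**What the plan says.** SAP 6.4 adds a categorical table to the by-visit ECG summaries: "the number (percentage) of subjects with at least 1 post-baseline abnormal ECG result in corrected QT interval", PR, QRS or heart rate. It lists eleven categories and describes them as clinically abnormal results.

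- Nine are absolute values: three for QTcF (the lowest is "QTcF interval >450 msec"), two for PR, two for QRS and two for heart rate.
- Two are changes, the smaller being "QTcF interval increases from baseline >30 msec" and the larger an increase of more than 60 msec.

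The PR, QRS and heart-rate cut-offs are printed under the heading for QTcF change from baseline, although they are absolute values.

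The rest of 6.4 handles baseline as follows. For quantitative parameters, "the average of the triplicate 12-lead ECG measurements will be used for the determination of baseline". Actual values and changes are summarised at each time point. "Shift from baseline in ECG interpretation and clinical significance will be summarized by visit", that is, on the investigator's reading and not on the numeric cut-offs. All ECG data are listed, with a further listing for participants with an abnormal post-baseline QTcF.

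Under SAP Section 6, "All analyses of safety data will be conducted using the Safety population". On entry, Protocol 4.1.2 excludes "History of or current abnormal ECG that is clinically significant, including atrial fibrillation" and certain conduction and ischaemic findings, but it sets no QTcF, PR, QRS or heart-rate limit. Protocol Section 2, Table 1 names the primary safety endpoint for this domain as "Changes in ECGs from baseline over time".

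**The concern.** A count of participants with at least one abnormal value after baseline answers a safety question only if abnormality before baseline is taken into account. Here it is not. Someone who enters with a resting heart rate of 56 or a QRS of 104 msec is eligible under the ECG criterion unless the finding is judged clinically significant. If the same value recurs at any later ECG, that participant is counted.

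The trial has no control arm, so each participant's own baseline is the only comparator. The endpoint is framed as change from baseline, and for adverse events SAP 6.1 requires that the event be absent before exposure or worsen afterwards. The nine absolute ECG categories apply no such condition. The percentages in that table will therefore mix pre-existing findings with new ones, and the table gives no means of separating them.

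**Working it through.** **The plan's own figure.** The documents state no expected ECG rate. The only planning figure is the chance of at least one finding among 40 participants, 1 − (1 − p)^40. For p = 0.1%, 1%, 5% and 10% this gives 3.92%, 33.10%, 87.15% and 98.52%, which agrees with the 3.9%, 33.1%, 87.1% and 98.5% in SAP 2.1. It confirms 40 as the planned denominator and says nothing about the ECG table.

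**Weight of one participant** (meets a cut-off at baseline and again later, no new onset):

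- All participants: 1/40 = 2.5 points.
- *C9orf72* cohort, if filled to its limit of 20: 1/20 = 5.0 points.
- Asymptomatic *GRN* cohort: Protocol 3.1 admits asymptomatic participants only from AL001-1, and Protocol 1.2.2.1 says six were enrolled there. With at most six, the weight is at least 1/6 = 16.7 points.

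**Rate for one absolute cut-off.** Let b be the share meeting the cut-off at baseline, q the share of those who meet it again afterwards, and e the rate of newly meeting it among the rest. Then:

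- rate as written = b·q + (1 − b)·e
- rate among those not meeting it at baseline = e
- difference = b·(q − e)

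The documents give none of b, q or e, so every value below is an assumption for illustration, with N = 40.

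| b | e | As written, q = 1 | As written, q = 0.8 | Newly meeting |
|---|---|---|---|---|
| 5% | 0 | 5.0% | 4.0% | 0/38 |
| 10% | 0 | 10.0% | 8.0% | 0/36 |
| 20% | 0 | 20.0% | 16.0% | 0/32 |
| 30% | 0 | 30.0% | 24.0% | 0/28 |
| 5% | 5% | 9.8% | 8.8% | 5% |
| 10% | 5% | 14.5% | 12.5% | 5% |
| 20% | 5% | 24.0% | 20.0% | 5% |
| 30% | 5% | 33.5% | 27.5% | 5% |

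Worked row: b = 20%, q = 0.8, e = 5% gives 0.20 × 0.8 + 0.80 × 0.05 = 0.16 + 0.04 = 20%, against 5% newly meeting. If b = 0 the two rates coincide. The two QTcF-increase categories are measured from baseline, so they cannot already be met there and the formula does not apply to them.

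**The case against.** The strongest reply is that baseline is dealt with elsewhere and that this table is only an addition. Protocol 8.4.2.7 asks for values and changes by time point, a shift table on interpretation and a listing of QTcF prolongation of grade 3 or higher, and it does not require threshold counts. SAP 6.4 supplies change-from-baseline summaries for the quantitative parameters and full listings. Under Protocol 7.3, a confirmed ECG finding that the investigator considers clinically significant is reported as an adverse event, and the treatment-emergent definition then applies. The analysis is descriptive, without formal testing.

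This stands as far as severity goes. A reader might infer that the primary ECG endpoint is left unanalysed, but the by-visit changes deliver it. A reader might also infer that the SAP presents these counts as treatment-emergent, but it never uses that term for them. What the reply does not do is repair the table. Group summaries do not show who newly crossed a cut-off, the shift table uses a different classification, and the dedicated abnormal listing covers QTcF only. For PR, QRS and heart rate, baseline status would have to be rebuilt from the full listing.

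A second objection is that a count of new onset alone would drop a participant whose heart rate falls from 58 to 42. That is correct, and it is why the fix includes a cross-tabulation.

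A further argument that might tempt a reader is that repeated ECGs drive up the count through chance crossings. It should not be used here. It needs independence between ECGs from the same person, including those before and after one infusion, which the documents do not support. It also mostly describes people below the cut-off at baseline, whom a baseline condition would still count.

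**Conclusion.** The point holds for the nine absolute cut-offs and for any overall abnormal count built on them. It rests on the SAP's silence about baseline status together with an eligibility criterion that sets no numeric limit. The SAP does not expressly say that such participants are to be included. The certain part of the size is the weight per participant: 2.5 points overall at 40, and at least 16.7 points in the asymptomatic *GRN* cohort if no more than six enrol.

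The total inflation is unknown. A reader might take the illustration to mean that the table starts 10 to 30 points too high. The documents do not support that, because they give no baseline prevalence for any cut-off. In particular, no inflation is shown for QTcF >480 or >500 msec, and Protocol 4.1.2 excludes clinically significant ECG abnormality and risk factors for ventricular dysrhythmia.

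Severity is minor: the output is descriptive, and no test, sample size or decision rule depends on it. It is still worth changing, because the table belongs to a primary safety domain and the correction is nearly free.

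**What to change.** Amend SAP 6.4 as follows.

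1. For each absolute cut-off, cross-tabulate baseline category against worst post-baseline category, using the mean-of-triplicate baseline already defined. Treat the low and high directions of PR, QRS and heart rate separately.
2. Report the number and percentage newly meeting the cut-off, with participants who did not meet it at baseline and have at least one post-baseline ECG as the denominator.
3. Keep the all-participant count as a second column.
4. Give PR, QRS and heart rate their own heading, apart from QTcF change from baseline.

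The cost is SAP wording and one table shell, on data already collected. The downside is that denominators will vary by cut-off and be small in small cohorts, so counts should be shown beside percentages. The cross-tabulation keeps participants with an abnormal baseline in view and, for QTcF, shows movement between grades. PR, QRS and heart rate have only one cut-off per direction, so how far such a participant worsens must still be read from the listings.
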